## 3.2 Bias Minimizing

### 3.2.1 Randomization (allocation)

To allocate the participants, we designed a specific software to calculate the sample and each block size, the number of recruiting centers, and the intervention arms ratio. We will use the stratified block randomization method to equally allocate subjects from the same strata to each group.

The total sample size in two cohorts is considered 24000 divided into eight cities (i.e., 3000 volunteers in each vaccination site). Each block includes 20 vaccine vials and five placebo vials randomly distributed within the block. Each vial has a label with a universally unique ID (UUID) and a one-digit code for the designated city, while the allocated blocks to each city are labelled with numbers from 1 through 140. Therefore, the volunteer UUID includes five digits, the first one is set for the city (vaccination center), and the next four digits depict a number from 1 through 3000, so all those UUIDs are unique in this study.

Knowing the sample size in each center and the block size, the software computes the necessary number of blocks and constructs a random chain for each block based on the algorithm suggested by Magalhães et al. (9). Briefly, in this method, at first, a list of intervention and placebo UUIDs is constructed. For example, in a 6-member block and 1:1 ratio of groups, the intervention list is organized as [0,0,0,1,1,1], then the list indices are randomly incorporated, and the list is organized based on the new order of indices. The indices are sorted based on a randomized process, in which in each step, one of the indices is selected via homogeneous distribution and added to the final sort-out and omitted from the non-selected indices. This process is repeated for each block. The randomization program is written in Python 3.8.2. For the construction of random numbers, we applied the Mersenne Twister algorithm, and the seed of randomization in that program is determined with a computer clock when the program runs. Every report file is named using date, and for validation purposes, the checksum of its content is calculated with the MD5 method and is kept in a separate file.

Allocations and trial management were performed using an online platform. The vaccine and placebo vials were identical and indistinguishable in appearance.

### **3.2.2 The process of assigning UUID to the subjects**

The orders of universally unique identifiers (UUID) are in the software and are inaccessible to the researcher. Study information is collected and managed through a web system developed by the knowledge-based company "Vista Technology Ideas Group." One copy of the randomly allocated list is given to Iran's FDA. The UUIDs are printed on adhesive labels. Those labels are attached to each volunteer's vaccine vials. After receiving informed consent and preliminary examination, eCRF will be completed for the volunteer. After completing eCRF and if the volunteer is considered "eligible for the study," a random identifier will be allocated to him/her and recorded. For the whole duration of the study, the UUID will be applied to all planned processes. As mentioned before, the assigned UUID is a 5-digit number the first digit is the city code, and the remaining four digits could be a number from 0001 to 3000.

### **3.2.3 Allocation concealment**

Allocation concealment will be using central allocation. A central team will perform subject assignments. After randomization, each participant will receive one out of 25 codes in the assigned block. The codes will not be clear for the participants and study teams at each site.

### **3.2.4 Blinding**

The UUIDs will be delivered to a group in charge of labelling the vials. None of the people in the vial-labelling group would have a role in recruiting study subjects or vaccine injection. They do not have any contact with the recruitment and vaccination site staff either. Thus, when sending the vial blocks to vaccination sites, no investigator can differentiate the vaccines from placebo vials. The suspensions in the vaccine and placebo vials are milky white and similar in colour and clarity. Moreover, vaccine and placebo vials are offered in similar appearance, they are inseparable, and packaging and will be placed in boxes of 25 vials on each box, the block number and serial numbers of vaccines/placebos are written. This process yields in the blindness of the study participants, vaccinators, investigators, and monitors.

Vaccinators will check the assigned UUID to each volunteer with the UUID labelled on the vial. All used vials in the study will be archived and kept secure.

## **3.3 Reasons for unmasking UUIDs**

In case of any emergency (such as the occurrence of SAEs), unmasking will be undertaken urgently. Just one investigator is authorized for urgent unmasking with the aid of the developed

online platform. The Co-PI is fully responsible for unmasking the volunteer's treatment group. The health and safety of volunteers is the most important consideration in Co-PI's decision-making about this issue. For this purpose, Co-PI will enter the electronic platform under emergencies, log into the electronic platform, open his page and send his request for opening the subject's UUID with a justification of the reasons to do that. This request will be submitted to the PI and the investigator authorized to unmask under emergency conditions. The last one will log into his page on the electronic platform and concur with the unmasking, then let the CoPI know the intervention group of the volunteer. All information on the unmasking will be recorded within the electronic platform. Afterwards, related sheets to inform the sponsor, national ethics committee and the national regulatory authority (FDA) will be filled out and submitted. The investigator in charge of unmasking will inform the sponsor for permission before opening the UUID unless delay threatens the affected volunteer. The date and reason for decoding UUID will be recorded in eCRF. Elderly people over 65 years of age, who are at high risk of contracting severe forms of the disease, will be proactively contacted if they are prioritized to receive the vaccine according to the national vaccination document and the announced policies of the National Corona Headquarters, and the intervention group they will be informed and in the case of the control group, they will be informed about providing them access to the vaccine of the national vaccination program.

In the case of other groups that are prioritized to receive vaccines according to the national vaccination document, the policies announced by the National Corona Headquarters and the current programs of the country, upon their request, the code will be decoded and their treatment group will be informed.

If the candidate has received one or two doses of the current vaccine and is prioritized for general vaccination with other vaccines, it is recommended that he remain in the current study and perform subsequent injections with the vaccine. However, if they want to withdraw from the study with their consent and inject another vaccine, the program administrator is only responsible for the vaccine received in this program and the consequences of the change. The vaccine will be their responsibility and the financial sponsor of the program (sponsor) will not be responsible for it.

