#### **4.3.1 Adverse Events (AEs)**

The AE is defined as any untoward medical events in participants that are temporally associated with the use of study interventions, whether or not considered related to vaccine/placebo. An AE can vary from clinical manifestations to abnormal test results.

After each injection, systemic and local pre-defined AEs will be registered using an online platform within three days. Solicited local AEs occur in the injection site and include pain, redness, swelling, induration, and warmth. Solicited systemic AEs are fever, chills, nausea, vomiting, malaise, fatigue, headache, diarrhea, pain in extremities, and rashes. Participants will record all these events using an online platform within three days after receiving each dose of vaccine or placebo. If any volunteer will not complete the diary, an active follow-up will be done on day four. Moreover, other unspecified symptoms (unsolicited AEs) will be followed up 28 days after each injection.

Serious Adverse Events (SAEs) are defined as any event which leads to a dangerous situation, hospitalization, longer duration of hospital stays, serious/permanent disability, congenital anomalies, requires a medical or surgical intervention to prevent permanent injury, or culminates in death. These events will be monitored up to five months after the last dosage of vaccine/placebo.

Medically Attended AEs (MAAEs) are adverse events after taking intervention that requires presentation to a health care provider, such as a general practitioner or emergency room visit for physical examinations. These events will be monitored up to five months after the last dosage of vaccine/placebo.

For monitoring and managing of AEs, the following measures will be performed:

- Active monitoring of participants for adverse events for half an hour after receiving each dose at vaccination sites.
- An Emergency medical services (EMS) ambulance will stand with three paramedics. There is an attending emergency medicine specialist with all first-aid and resuscitation equipment in place

All arrangements and coordination have been made with a supporting hospital in each city to transfer and visit participants who might suffer SAEs. In case of any SAE, the emergency specialists of the study will coordinate with the hospital an appointment for participants. We will provide 24-hour free-of-charge medical services in these hospitals for participants during the study.

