- The solicited AEs (local and systemic) are recorded in online diary forms up to 72 hours after receiving each dose by volunteers. If any volunteer does not complete the diary, an active follow-up will be done on day fourth. During this period, medical services and consultations, and hospitalization are provided to volunteers who are affected by AEs.
- Passive monitoring of unsolicited AEs from the first day until day 28th is done through spontaneous reporting by participants to call centers or go to specified hospitals.
- SAEs and MAAEs are detected passively whenever a volunteer report to the call center or consults with the hospital. These participants will be followed actively until fully recovered.
- All SAEs and MAAEs should be reported at the earliest time possible (a few days) to the sponsor and PI, who will inform DSMB to decide about unmasking and withdrawing the participants from the study.
- In case of any SAE or fatal event that needs hospitalization, the CoPIs will report the case to the Pasteur Institute of Iran via an urgent phone call, which in turn reports to FDA, and the National Ethics Committee (NEC).

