## Secondary outcomes

Outcome	Definition	Measurement method	Timing of measurement
Severe COVID-19 infection	Includes severe, critical or hospitalized COVID-19 cases	Included those COVID-19 patients with O 2 saturation level $\leq 90\%$ , evidence of lower respiratory disease (e.g., shortness of breath, chest pain or chest tightness) with or without fever $\geq 38^{\circ}\text{C}$ during clinical assessment or imaging, tachypnea (i.e., respiration rate $>30$ breaths/min), increased P(A-a) O 2 gradient, lung infiltration $>50\%$ in CT-scans, PaO 2 /FiO 2 $<300$ mmHg, or acute worsening of respiratory symptoms especially dyspnea, respiratory failure, septic shock, and/or multiple organ dysfunction, hospitalization or death due to COVID-19.	
C1: From day 14th after the 2nd dose until the end of efficacy study time
 
C2: From day 14th after the 3rd dose until the end of efficacy study time

COVID-19-related death	Based on the WHO definition: The death of a COVID-19 case is not attributable to another cause (e.g., trauma). There should not be a recovery interval between COVID-19 infection and death	Based on the diagnosis of PI and Co-PIs in the cities and approval of DSMB	
Humoral immunity	At least a 4-fold rise in Anti-S1 IgG titer in serum sample compared to the baseline	ELISA	28 days month after the last vaccine shot compared to the serum titer of Day 0
Virus neutralization	Detection of antibodies which can inhibit virus replication (an antibody, which can neutralize virus infectivity)	VNT (Virus Neutralization Test)	On days 0 and 28 days after the second dose, serum samples will be taken from a subset of antibody-positive volunteers and the neutralizing antibody titer will be determined

Cell-mediated immunity (CMI)	Measuring Interferon Gamma secreted from PBMC (peripheral blood cells mononuclear cell)	Interferon Gamma Release Assay (IGRA)	In the cities of Babol and Sari, CMI will be performed
Safety	Frequency of local and systemic adverse events disaggregated by intensity (degree) and seriousness (type)	Case investigation form, Diary form, telephonic follow-up	From day 0 until 5 months after the last dose

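### A Co-PI told a participant's arm after a serious adverse event may also diagnose that participant's COVID-19-related death, so blinded assessment of this endpoint is not protected

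*Protocol*

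**What the plan says.** Five parts of the protocol bear on this.

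- **Trigger (3.3).** "In case of any emergency (such as the occurrence of SAEs), unmasking will be undertaken urgently". SAEs are the example given.
- **Procedure and recipient (3.3).** The Co-PI, who is given full responsibility for unmasking, files a reasoned request. It goes to the PI and to the one investigator authorised to open codes in an emergency. That investigator must agree, must seek the sponsor's permission unless waiting would endanger the participant, and will "then let the CoPI know the intervention group of the volunteer".
- **What counts as an SAE (4.3.1).** "Serious Adverse Events (SAEs) are defined as any event which leads to a dangerous situation, hospitalization, longer duration of hospital stays", and also an event that "requires a medical or surgical intervention to prevent permanent injury, or culminates in death". On duration: "These events will be monitored up to five months after the last dosage of vaccine/placebo".
- **Who decides (4.3.1).** SAEs and medically attended events are reported to the sponsor and PI, "who will inform DSMB to decide about unmasking and withdrawing the participants from the study".
- **Who diagnoses the endpoint (secondary outcomes table).** COVID-19-related death is measured as follows: "Based on the diagnosis of PI and Co-PIs in the cities and approval of DSMB". The row for severe COVID-19 lists criteria and names no assessor.

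Section 3.2.4 states that investigators are blinded.

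**The concern.** A COVID-19 hospitalisation or death is both an efficacy event and an SAE, and an SAE is a stated reason to open the code. The role that receives the code is one of the roles that diagnose COVID-19-related death. That diagnosis is partly a matter of judgement, because the assessor must decide whether something other than COVID-19 explains the death.

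Vaccine efficacy against COVID-19-related death is a stated secondary objective. If attribution is made with the arm known, it can shift between arms; attributing vaccine-arm deaths to other causes, for example, would raise the efficacy estimate. The exposure falls on the participants who supply the events, so a large and otherwise well-blinded trial does not dilute it.

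**Working it through.** No figure in the protocol depends on this point, so the check is a side-by-side reading.

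1. **Do endpoint events meet the SAE definition?** Yes. Section 4.3.1 includes hospitalisation and death. Section 4.1.1 and the secondary outcomes table count hospitalisation or death due to COVID-19 as severe disease, and COVID-19-related death is a separate outcome. No section exempts endpoint events.
2. **Do the time windows overlap?** Yes. SAEs are followed for five months after the last dose. Section 6.2.5 ends efficacy follow-up three months after the second dose in C1 and four months after the third in C2. The SAE window covers both.
3. **Who learns the arm?** Under 3.3 the authorised investigator opens the code and tells the Co-PI. The PI receives the request, but the text does not say that the PI is told the arm.
4. **Who judges the death?** The PI and Co-PIs, with DSMB approval. The protocol does not say whether the DSMB is blinded.
5. **Can disclosure come before the diagnosis?** The protocol fixes no order. If a participant is unmasked during a hospital stay and later dies, disclosure necessarily precedes the death diagnosis. No rule removes that Co-PI from it.
6. **Is there another safeguard?** The committee in section 4.3.2 classifies SAEs and medically attended events by causal association with immunisation. It is not given the task of confirming efficacy endpoints, and its blinding is not stated.
7. **Do the two rules on unmasking agree?** Section 3.3 puts the responsibility on the Co-PI, with the authorised investigator's agreement. Section 4.3.1 gives the decision to the DSMB. Both apply to SAEs.

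**Scale.** The protocol gives no death rate and no expected share of cases unmasked, so no bias can be computed. For context only, the design incidences in section 6.1 imply 3,600 × 0.012 + 1,200 × 0.018 = 43.2 + 21.6 = 64.8, about 65 symptomatic placebo cases over the two- and three-month design periods before dropout. With the monthly rate of 0.0055 the figure is 3,600 × 0.011 + 1,200 × 0.0165 = 39.6 + 19.8 = 59.4, about 59. The protocol calls the incidence a minimum, and follow-up in section 6.2.5 is longer, so actual numbers could be higher. If deaths are only a fraction of such cases, a few attribution decisions could matter.

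**The case against.** The strongest reply is that section 3.3 does not unmask automatically. A reader might infer from its opening sentence that every SAE, and so every hospitalised or fatal COVID-19 case, is unmasked. The procedure that follows does not support this. It requires a reasoned request, agreement by a second person and, unless waiting is dangerous, sponsor permission, and it is recorded. That stands: blinding is lost only for participants who are actually unmasked. But these steps govern whether the code is opened, not what its recipient may do afterwards.

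A reader might also infer that severe COVID-19 loses blinded assessment. The documents do not support that. No assessor is named, and several criteria are measurements (oxygen saturation, respiratory rate, PaO2/FiO2). A hospitalisation due to COVID-19 also meets the definition before any unmasking that it prompts. What remains open is whether the hospitalisation is attributed to COVID-19.

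Nor does the text show that the PI is unblinded, since receiving a request does not reveal the arm. The PI shares the death diagnosis and the DSMB must approve it. This tempers the concern without removing it, because the Co-PI still contributes to the diagnosis and the DSMB's blinding is not stated.

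Finally, sections 3.3 and 4.3.1 could be read as an urgent and a non-urgent route. That is plausible, but the protocol does not say so, and SAEs fall under both.

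**Conclusion.** The point holds for COVID-19-related death in participants whose code was opened. As written, a person who knows the arm may help decide a judgement-based endpoint, and the investigator blinding claimed in section 3.2.4 does not extend to those cases. For severe COVID-19 the exposure is limited to attributing a hospitalisation to COVID-19, and with no assessor named this is a gap, not a demonstrated breach. The rules on who decides about unmasking conflict and need reconciling.

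Neither the size nor the direction of bias can be stated. Both depend on how many endpoint cases are unmasked before classification and how often knowledge of the arm changes a decision, and the protocol gives neither. The conclusion assumes only that some participants are unmasked after an SAE before their death is classified, which the protocol permits. The PCR-confirmed primary outcome is not challenged. This is a change that should be made, but it concerns a secondary objective and can be met by wording.

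**What to change.** 1. In the secondary outcomes table, require that COVID-19-related death, and any judgement that a hospitalisation is due to COVID-19, be classified by existing personnel who do not hold that participant's code, from a case file without the code. Co-PIs of other cities could do this, or the committee in section 4.3.2 if the protocol states that it is blinded. Exclude any Co-PI who received the code for that participant.
2. Report how many endpoint cases were unmasked before classification.
3. Reconcile sections 3.3 and 4.3.1 on who decides about unmasking. Reconcile the SAE wording in 3.3 with the endpoint definitions in 4.1.1 and the secondary outcomes table. Leave access to the code for participant care unchanged.

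The cost is protocol wording and the preparation of case files without the code. No extra participants or procedures are needed. The small downside is that classification may take slightly longer.

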## **4. Study Procedures and Assessments**

### **4.1 Efficacy Assessment**

The vaccine efficacy will be considered in terms of the prevention of symptomatic COVID-19 infection (as the primary outcome), as well as severe COVID-19 infection and COVID-19-related

death (as secondary outcomes), all of which will be considered in efficacy analysis if they occurred from 14 days after the second/third dose onward.

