#### **4.1.1 Case Definition**

o **Symptomatic COVID-19 infection** is defined as those presenting with two or more of the following symptoms lasting for over 24 hours confirmed with a positive RT-PCR testing: Fever (temperature  $\geq 38^{\circ}\text{C}$ ), chills, new cough, sore throat, nasal congestion, fatigue, muscle or body pain, headache, nausea or vomiting, diarrhea, loss of smell or taste, or at least one respiratory sign or symptom (i.e., cough, shortness of breath, or clinical or radiographic evidence of pneumonia).

o **Severe COVID-19 infection** will be considered as O2 saturation level  $\leq 90\%$ , evidence of lower respiratory disease (e.g., shortness of breath, chest pain or chest tightness) with or without fever  $\geq 38^{\circ}\text{C}$  during clinical assessment or imaging, tachypnea (i.e., respiration rate  $>30$  breaths/min), increased P(A-a) O2 gradient, lung infiltration  $>50\%$  in CT-scans, PaO2/FiO2  $<300$  mmHg, or acute worsening of respiratory symptoms especially dyspnea, respiratory failure, septic shock, and/or multiple organ dysfunction, hospitalization or death due to COVID-19.

o **COVID-19-related Death** will be considered based on the WHO definition: deaths not attributable to another cause (e.g., trauma). There should not be a recovery interval between COVID-19 infection and death.

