#### **4.3 Safety Assessment**

Whether solicited or unsolicited, the local and systemic adverse events (AEs) will be recorded in diary forms by the volunteers. The AEs will be recorded from the first dose (Day 0) until five months after the last dose in both cohorts.

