## **6.2 The Statistical Analysis Plan**

### ***6.2.1 Efficacy population***

To analyze the efficacy, we will apply by “Intention to treat (ITT)” analysis.

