### ***6.2.5 Analysis of efficacy***

Considering the high incidence of COVID-19 in Iran and the high sample size of the study, the duration of follow-up for the efficacy analysis in C1 is estimated to be four months (3 months after the second dose) making it possible to estimate the efficacy with a significance level of  $\alpha$

<0.0001. The study duration for safety analysis in C1 is six months. Also, the duration of follow-up for the efficacy analysis in C2 is estimated to be six months (4 months after the third dose). Such a duration brings a possibility to estimate the efficacy with a significance level of  $\alpha < 0.0001$ . The study duration for side effect analysis in C2 will be seven months (or five months after the third dose).

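### Severe COVID-19 and COVID-19 death are counted from day 14 after the last dose with no link to when the illness began, so deaths from earlier illness enter the efficacy estimate and the date of a severe case is left open

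*Protocol*

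**What the plan says.** Section 4.1 names symptomatic infection as primary, and severe infection and COVID-19-related death as secondary, then gives all three the same rule: "all of which will be considered in efficacy analysis if they occurred from 14 days after the second/third dose onward". The outcome table runs the severe outcome from day 14 after the second dose (C1) or third dose (C2) "until the end of efficacy study time". In the text at hand the timing cell of the death row is blank, which may be a merged cell lost in extraction.

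Section 4.1.1 defines severe disease by clinical state, up to "septic shock, and/or multiple organ dysfunction, hospitalization or death due to COVID-19". Death is tied to an unrecovered infection: "There should not be a recovery interval between COVID-19 infection and death". Neither definition says when that infection must have begun.

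Section 6.2.1 states "To analyze the efficacy, we will apply by “Intention to treat (ITT)” analysis", and no exclusion is given for illness starting between the last dose and day 14. Section 4.3 follows adverse events "until five months after the last dose in both cohorts". Note 3 under Table 1 and note 3 under Table 2 count every PCR-positive case after the second shot towards the primary outcome, without the 14-day lag.

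**The concern.** A 14-day lag serves to keep illness acquired before the regimen is expected to protect out of the efficacy estimate. Severe disease and death follow the start of illness by days or weeks, so a lag applied to the date of the outcome does not achieve this.

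Take a participant who falls ill on day 8 after the last dose and dies on day 22. Under section 4.1 the illness precedes the primary window, yet the death counts in the efficacy analysis. Deaths are then no longer a subset of the primary cases. For severe disease, two analysts could date the same case differently and both comply with the text. Efficacy against severe disease and against death are two stated secondary objectives, and the dating rule decides which events enter them.

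**Working it through.** The protocol gives no figure for this point, and the assumptions in section 6.1 name no severe or fatal outcome, so there is no stated number to reproduce. The sample size is unaffected. What follows is an illustration.

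**Inputs from the protocol.** Counting starts at day 14 after the last dose (4.1). Efficacy follow-up ends three months after dose 2 in C1, taken as day 91, and four months after dose 3 in C2, taken as day 122 (6.2.5). Section 6.1 assumes efficacy of 50% (C1) and 70% (C2).

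**Assumptions not in the protocol.** The onset rate is constant and the lag L from onset to severe outcome or death is fixed at 7, 14 or 21 days. No counted illness begins before the last dose, since section 2.4 bars a further dose after a positive PCR. Outcomes are dated by their own occurrence.

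**Step 1: share of counted placebo events with onset before day 14.** With the window closing on day W, counted onsets run from max(0, 14 − L) to W − L. The share is f = [14 − max(0, 14 − L)] / [W − L − max(0, 14 − L)].

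| L (days) | C1, W = 91 | C2, W = 122 |
|---|---|---|
| 7 | 7/77 = 9.1% | 7/108 = 6.5% |
| 14 | 14/77 = 18.2% | 14/108 = 13.0% |
| 21 | 14/70 = 20.0% | 14/101 = 13.9% |

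Two sensitivities. If onsets before the last dose were also carried in, the 21-day figure for C1 would be 21/77 = 27%. Table 2 ends C2 efficacy monitoring at Month 5, against six months in section 6.2.5. A counting window of about 80 days would then give 7/80 = 8.8%, 14/80 = 17.5% and 14/73 = 19.2% for C2.

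**Step 2: effect on reported efficacy.** For rare events, reported VE = (1 − f) × VE + f × VE_early, where VE_early applies to illness starting before day 14.

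| Case | VE_early | L = 7 | L = 14 | L = 21 |
|---|---|---|---|---|
| C1, VE 50% (6.1) | 0% | 45.5% | 40.9% | 40.0% |
| C1, VE 50% (6.1) | 25% | 47.7% | 45.5% | 45.0% |
| C1, VE 80% (assumed) | 0% | 72.7% | 65.5% | 64.0% |
| C1, VE 80% (assumed) | 40% | 76.4% | 72.7% | 72.0% |
| C2, VE 70% (6.1) | 0% | 65.5% | 60.9% | 60.3% |
| C2, VE 70% (6.1) | 50% | 68.7% | 67.4% | 67.2% |

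The last row borrows the 50% that section 6.1 assumes for two doses, because C2 participants have had two doses before the third. If VE_early = VE, the formula returns VE and there is no dilution.

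**Step 3: the end of the window (C1).** Among illnesses with onset from day 14 to day 91, the share whose outcome falls after day 91 is L/77: 9.1%, 18.2% and 27.3%. Earlier illnesses carried in at the start add min(L, 14)/77: 9.1%, 18.2% and 18.2%. The net loss of placebo events is 0, 0 and 7/77 = 9.1%.

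**The case against.** The best reply is that section 4.1 leaves a date undefined; it does not lay down a wrong rule. A reader might infer that the protocol expressly dates severe disease by progression and symptomatic disease by onset. It does neither. One verb covers all three outcomes, no passage dates any of them at onset, and a severe infection can be said to occur when the infection does. That stands, so for severe disease the fault is ambiguity. It does not rescue death, which occurs on its own date.

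A reader might also infer that the day-8 illness in the example is certainly not a primary case. Under the notes to Tables 1 and 2 it would be one, so whether deaths remain a subset of primary cases depends on how that conflict is settled.

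Nor do the documents establish that deaths after the efficacy cut-off are dropped. Section 4.1 gives no end date, and the closing date stands in the severe row only. Even where the cut applies, it acts alike in both arms and does not by itself bias the hazard ratio. For lags up to 14 days the events lost at the end are replaced at the start.

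Finally, the lags and early efficacies are assumptions, the bias usually runs against the vaccine, and only secondary outcomes are touched. All of that is right and limits the weight of the point. Deferral to an analysis plan is a weaker answer, because the protocol itself states the counting rule and the timing column.

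**Conclusion.** The point holds in limited form. For COVID-19 death, the literal rule admits deaths from illness that began before day 14. For severe COVID-19, the protocol does not say which date decides. Given the lags, constant onset rate and windows assumed above, such illness supplies about 9% to 20% of counted placebo events in C1 and 6.5% to 14% in C2 with a four-month window.

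Reported efficacy usually falls as a result. At the section 6.1 efficacies the fall is up to about 10 points with no early protection, 1 to 3 points in C2 if two doses already give 50%, and nil if early protection is full. The end cut mainly changes which events are counted. The primary analysis and the sample size do not change.

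**What to change.** In section 4.1 and the timing column of the secondary outcome table, including the death row, state that severe COVID-19 and COVID-19 death count only when the causative PCR-confirmed episode had symptom onset at least 14 days after the last dose and before the efficacy cut-off. Add symptom-onset date to the eCRF. The case definition already depends on symptom duration, but no passage lists onset date as a recorded item.

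Ascertain progression of those episodes through the existing follow-up to five months after the last dose. That leaves about two months beyond the efficacy cut-off in C1 and one month in C2 on the section 6.2.5 timings. Section 4.3.1 already follows participants with serious or medically attended events until recovery, and the table notes provide daily calls to non-hospitalised positives.

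Reconcile note 3 of Tables 1 and 2 with section 4.1, and the C2 end of efficacy monitoring in Table 2 with section 6.2.5.

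The cost is a few sentences and one data field. Final severe and death counts would be available slightly after the efficacy cut-off.
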